5.5.5 Permitted dose adjustments of study treatment

This section describes the actions that are required if a systolic BP decrease (i.e. <5th percentile for age) occurs during the administration of study drug and is confirmed by two measurements taken 10 minutes apart (in patients with intermittent BP measurements) or by a consistent measurement over ≥ 5 min (in patients with invasive continuous BP measurements). This event is considered a “systolic blood pressure decrease event” (SBPDE) and must be recorded as such on the appropriate eCRF.

If the SBP falls to <5th percentile for the age of the patient ([AHA PALS guidelines 2010, Kleinman 2010](#), see [Appendix 4](#)) and is a confirmed SBPDE per the criteria in the previous paragraph, then the following steps are required:

1) In all patients:

Assess the patient and treat alternative causes of hypotension (consider hypovolemia, arrhythmia, heart-lung interactions, concomitant medications, pneumothorax or pericardial tamponade, hardware malfunction or measuring error etc.)

2) As clinically indicated, the following steps should be taken, preferentially in the indicated order (however, the options can be applied in sequence or separately at the investigator's discretion):

1. Increase the infusion rate of inotropic and/or vasoactive drugs as clinically indicated up to a vasoactive score of 20 and/or
2. Reduce the serelaxin infusion rate by 50% and/or
3. Discontinue serelaxin infusion

Patients who tolerate the reduced serelaxin infusion rate should remain on this reduced infusion rate for the remainder of the 48 hour infusion period, as tolerated. The exact time and date of the reduction of the study drug infusion rate must be recorded on the Drug Administration Record case report form. All assessments, including PK sampling, should continue per protocol even if the dose rate is reduced. Time from initiation of study drug infusion to completion must not exceed a total of 48 hours.

Dosing may be discontinued at any time at the discretion of the investigator. Reasons for which the investigator may discontinue the study drug include, but are not limited to, serious or intolerable AEs suspected to be causally related to study drug. In the event that study drug

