The number and proportion of patients who experience a confirmed blood pressure decrease event during study drug administration will be provided by dose level within each dose group and age cohort. Further details on confirmed blood pressure decrease events (including whether they result in study drug dose reduction or discontinuation) will be provided as well.

ECG

The ECG findings and central ECG data will be summarized as appropriate by age cohort and dose group and for all subjects in the SAF population.

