[REDACTED]	[REDACTED]
SBPDE	Systolic Blood Pressure Decrease Event
CSR	Clinical Study Report
[REDACTED]	[REDACTED]
DBP	Diastolic Blood Pressure
ECG	Electrocardiogram
ES	Enrolled Set
FAS	Full Analysis Set
HR	Heart Rate
[REDACTED]	[REDACTED]
MedDRA	Medical Dictionary for Regulatory Affairs
[REDACTED]	[REDACTED]
PK	Pharmacokinetics
PT	Preferred Term
PSRC	Pediatric Safety Review Committee
Q1	the First Quartile
Q3	the Third Quartile
RR	Respiratory Rate
SAE	Serious Adverse Event

SAF	Safety Set
SBP	Systolic Blood Pressure
SCR	Screened Set
SOC	System Organ Class
[REDACTED]	[REDACTED]
[REDACTED]	[REDACTED]

1 Introduction

This document provides details of the statistical analyses to support the completion of the abbreviated Clinical Study Report (CSR) for the study CRLX030A2208. Due to the early termination of the study, the planned analyses for a full/complete CSR (as outlined in the study protocol) may not provide clinically and/or statistically meaningful results. Therefore, an abbreviated CSR is planned for the study CRLX030A2208. No efficacy analysis will be performed for the abbreviated CSR: PK parameters and other derived efficacy parameters (as defined in the study protocol) will not be provided; Non-derived efficacy parameters (as outlined in the study protocol), if available, will be listed at the individual patient level. Other data will be listed with the following exceptions:

Summary tables will be provided for the following non-efficacy data:

- Disposition (see [Section 5.1](#))
- Demographic and background characteristics (see [Section 5.3](#))
- Safety data
 - Treatment emergent non-serious AEs (see [Section 10](#))
 - Treatment emergent SAEs (see [Section 10](#))
 - Treatment emergent AEs (including non-serious AEs and SAEs) (see [Section 10](#))
 - Treatment emergent AEs leading to discontinuation (see [Section 10](#))
 - Deaths (see [Section 10](#))
 - Vital signs (selected) (see [Section 9](#))
 - Systolic blood pressure (SBP)
 - Diastolic blood pressure (DBP)
 - Heart rate (HR)
 - Respiratory rate (RR)

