5.4 Medical History

Medical history entered on the medical history CRF page at screening [REDACTED] will be coded using the MedDRA dictionary. Medical history and protocol solicited events (only for post-surgical patients) will be listed at the individual patient level for the SAF.

6 Study medication

Data entered on the Dosage Administration Record CRF page will be listed at the individual patient level for the SAF. This will include dose prescribed (ug/kg/day), start/end date and time of the infusion, concentration (ug/ml), rate of infusion (mL/h) and reason for the dosage administered.

7 Concomitant medication

Prior and concomitant medications, continuous intravenous concomitant medications, surgical and medical procedures and use of mechanical ventilator will be listed at the individual patient level for the SAF. The medication name will be coded using therapeutic class (ATC code) and preferred term (PT).

8 Pharmacokinetic (PK) data

PK concentration data will be listed at the individual patient level for the SAF. Invalid PK concentration data will be noted. A graphical presentation will be employed to show individual serelaxin concentration-time (actual) profiles by age cohort within each dose group. These figures will be prepared for the PK analysis set.

9 Selected vital signs for safety (SBP, DBP, HR and RR)

Summary statistics (n, mean, standard deviation, median, Q1, Q3, minimum, and maximum) will be provided by age cohort within each dose group for the measurement at each visit and change from baseline values for the following parameters for the safety population:

- Systolic blood pressure (SBP)
- Diastolic blood pressure (DBP)
- Heart rate (HR)
- Respiratory rate (RR)

10 Adverse Events (AEs), SAEs and Deaths

A treatment emergent adverse event is defined as an adverse event that occurs at or after the start of the study treatment. Treatment emergent adverse events including non-serious AEs, SAEs, AEs (including non-serious AEs and SAEs) and AEs leading to discontinuation will be

summarized descriptively (using number and percentage) by age cohort within each treatment group and in the overall group. Similarly, deaths will be summarized descriptively as appropriate. The number and percentage of these events will be presented by system organ class (SOC) and MedDRA preferred term (PT). All AEs will be listed at the individual patient level. These analyses will be performed for the SAF.

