In addition, SAEs in screen failure patients will be listed at the individual patient level.

11 Other data

Other data will be listed at the individual patient level as appropriate. The following data will be listed for the SAF, and listings marked with “*” will be subject to data availability:

- Local lab (including chemistry, hematology and urinalysis)
- Central lab (including chemistry and hematology)
- Vital signs and clinical assessment
- Ventilation/respiratory parameters (if on mechanical ventilation)
- * Systolic Blood Pressure Decrease Event (SBPDE)
- * Vital signs – SBPDE monitoring
- * Ventilation/respiratory parameters – SBPDE monitoring
- * Vital signs – AE suggestive of Worsening Heart Failure (WHF) monitoring
- * Ventilation/respiratory parameters – AE suggestive of Worsening Heart Failure (WHF) monitoring
- Echocardiography
- [REDACTED]
- ECG
- [REDACTED]
- [REDACTED]

[REDACTED] eGFR (as part of the central laboratory data) will be calculated using the Schwartz formula (Schwartz et al. 2009): eGFR (mL/min/1.73m²) = 0.41 x height (cm)/serum creatinine (mg/dL).

Mean arterial pressure, derived as [(2 x DBP) + SBP] ÷ 3 (Cywinski 1980), will be included in listings of the vital signs data. Notably abnormal vital signs (SBP, DBP, HR and RR) [REDACTED] will be noted in data listings.

12 Interim analyses

There will be no formal interim analysis for this study. However, there will be interim PK and safety data reviews by the Pediatric Safety Review Committee (PSRC). See Section 3.1 of the study protocol for study design details.

[REDACTED]

13 Sample size and power considerations

Sample size is guided by feasibility in pediatric patient studies for assessment of safety, tolerability and pharmacokinetics.

The sample size planned for the high-dose group (10/30/100 µg/kg/day) per age cohort will be 6 subjects or 3 subjects (see Section 3.1 of the study protocol v04 for the study design details). With a sample size of 6 subjects per age cohort, receiving RLX030 at various doses, there is ~80% probability to observe an adverse event with an underlying occurrence rate of 24% at least once for each cohort and dose combination during the study. With a sample size of 3 subjects per age cohort, receiving RLX030 at various doses, there is ~56% probability to observe an adverse event with an underlying occurrence rate of 24% at least once for each cohort and dose combination during the study.

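### The SAP replaces the protocol's count and proportion of patients with a confirmed blood pressure decrease event, by dose level, with a listing, and gives no reason specific to that event

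*SAP*

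**What the plan says.** Protocol 5.5.5 defines the event as a systolic pressure below the 5th percentile for age, confirmed by repeated or sustained measurement, and says that it "must be recorded as such on the appropriate eCRF". Protocol 9.5.2 then fixes the output, split by cohort and by low-dose or high-dose assignment: "The number and proportion of patients who experience a confirmed blood pressure decrease event during study drug administration will be provided by dose level". A separate sentence there covers the consequences for dosing: "Further details on confirmed blood pressure decrease events (including whether they result in study drug dose reduction or discontinuation) will be provided as well".

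The SAP (Module 3, Amendment 1) narrows the reporting. Section 1 begins its reason with "Due to the early termination of the study, the planned analyses for a full/complete CSR", and goes on to say that the planned analyses may not give meaningful results, so an abbreviated report will be written. It then introduces a closed list: "Summary tables will be provided for the following non-efficacy data". That list covers disposition, background characteristics, treatment-emergent adverse events, deaths and four vital signs. The blood pressure decrease event is not on it.

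Section 11 opens with "Other data will be listed at the individual patient level as appropriate". The entry "Systolic Blood Pressure Decrease Event (SBPDE" appears in that section with an asterisk, meaning that even the listing depends on data being available. Section 10 keeps adverse event tables by age cohort within treatment group: "The number and percentage of these events will be presented by system organ class (SOC) and MedDRA preferred term (PT").

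Addendum 1, dated after database lock, adds summaries of drug concentrations and of the secondary haemodynamic variables. It does not mention the event.

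**The concern.** Safety and tolerability is a primary objective (Protocol 2.1), and the design escalates dose within each patient. A fall in blood pressure is the one risk for which the protocol provides its own event definition, an age-specific threshold table (Appendix 4) and a handling section. Protocol 8.4 also names hypotension events, dose adjustments and discontinuations as expected items for the interim data reviews.

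For that event the protocol chose a specific summary: patients affected, by dose level, with the consequence for dosing. The SAP drops it without saying why a simple count is less meaningful than the adverse event counts it keeps. A reader of the report would have no tabulated numerator, denominator or zero statement for the event, and no table showing whether events clustered at particular infusion rates.

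**Working it through.** **The plan's own figure.** The only stated figure that bears on counting events is in Protocol 9.7 and SAP 13: the probability of seeing at least one adverse event whose true rate is 24%. The formula is 1 − (1 − 0.24)^n.

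- n = 6: 1 − 0.76^6 = 80.7% (stated ~80%)
- n = 3: 1 − 0.76^3 = 56.1% (stated ~56%)

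Both reproduce. The point disputes no number; it concerns which table exists.

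**Step 1. Commitment against plan.**

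| Element | Protocol 9.5.2 | SAP Module 3 | Addendum 1 |
|---|---|---|---|
| Patients with a confirmed event, n and proportion | Yes, by dose level within dose group and age cohort | Listing only, if data are available (Section 11) | Not added |
| Events leading to dose reduction or discontinuation | Yes | No table | Not added |
| Adverse events during each 16-hour dose period | Yes | Dropped; by age cohort within treatment group only (Section 10) | Not added |

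**Step 2. Do the retained tables substitute?**

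- *Adverse event tables.* These are by dose group. Each group runs through three nominal rates: 3, 10 and 30, or 10, 30 and 100 µg/kg/day. The range is tenfold in each (30/3 = 10; 100/10 = 10). A dose-group figure cannot place an event at a rate.
- *Coverage.* Under Protocol 7.1 an abnormal test result is an adverse event only if it causes signs or symptoms, is clinically significant or needs therapy. A confirmed event meeting none of these need not enter the tables.
- *Consequences.* The actions recorded for an adverse event in Protocol 7.1 include permanent discontinuation but not dose reduction. The adverse event data therefore do not show how often the rate was reduced.
- *By-visit systolic pressure (SAP 9).* Means and quartiles at scheduled times do not count patients who crossed an age-specific threshold.

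**Step 3. Can it be rebuilt?** Largely, by hand. SAP 11 lists the events and the associated monitoring. SAP 6 lists each patient's prescribed dose, infusion start and end times, rate and the reason for the dosage given. The listings do not supply denominators. A patient may repeat a level (Protocol 5.5.4), or have the rate halved or stopped (5.5.5), so exposure at each level has to be reconstructed patient by patient. Halving gives 1.5, 5, 15 and 50 µg/kg/day from 3, 10, 30 and 100, none of which is a nominal level.

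**Step 4. What precision would the table have?** Inputs are the planned cell sizes in Protocol 3.1: 3 per low-dose cohort, and 3 or 6 per high-dose cohort. That makes 4 × 3 = 12 low-dose patients and at least 3 + 3 + 6 + 6 = 18 high-dose patients. Intervals are exact (Clopper–Pearson) 95%; for zero events the upper limit is 1 − 0.025^(1/n).

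| n | 0 events | 1 event |
|---|---|---|
| 3 | 0 to 70.8% | 0.8 to 90.6% |
| 6 | 0 to 45.9% | 0.4 to 64.1% |
| 12 | 0 to 26.5% | 0.2 to 38.5% |
| 18 | 0 to 18.5% | 0.1 to 27.3% |

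The documents do not give enrolment at termination, so planned sizes are an assumption and actual cells may be smaller.

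**The case against.** The strongest reply is that this is a declared reduction in scope. The study stopped early, the SAP says so, and other planned safety summaries (laboratory data, exposure, concomitant medication) also became listings. With so few patients, a careful reader can count events, exposed patients and dose changes from the listings, and intervals this wide support no comparison between rates. Events that prompted treatment would probably also be reported as adverse events and so be tabulated.

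Much of that stands. The information is not lost; what is missing is the summary. A reader might infer that the trial will report no rate at all for hypotension. The documents do not support that: hypotension reported as an adverse event gets a number and percentage by preferred term, and systolic and diastolic pressure are summarised by visit. A reader might also infer that hypotension is a dose-limiting risk, or that safety by dose is itself a primary objective. Neither is in the documents. Protocol 3.6 reports slightly more hypotension-related events than placebo in adults, with no dose or exposure relationship, and the primary objective concerns the infusion, not its separate doses.

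What does not stand is early termination as the full explanation. Adverse event percentages are kept in the same small cells, and Addendum 1 later added descriptive tables for other data.

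**Conclusion.** The point holds as a gap between protocol and SAP. The protocol specifies a count and proportion for the confirmed event by dose level, with its dosing consequences; the SAP supplies a conditional listing, and the addendum does not restore the table. As planned, no table gives a rate for the protocol-defined event, and no adverse event table is by dose level.

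The effect on any reported result cannot be sized, because neither event counts nor actual enrolment is in the documents. On planned cell sizes a single-cell proportion is almost uninformative on its own (0/3 allows a true rate up to 71%, 0/6 up to 46%). The value of the table is complete descriptive reporting, including explicit zeros and correct denominators, and not inference about a dose trend.

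The conclusion assumes that SAP Section 1 lists every planned table, as it reads, and that redacted text does not hold an additional one.

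**What to change.** Add to SAP Sections 1 and 11 one descriptive table on the safety set:

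- n/N patients with a confirmed event by actual dose level at onset, within dose group and age cohort and overall;
- N is the number of patients who received that level;
- reduced or repeated rates are assigned by the actual rate on the dosing record, with any rate outside the nominal levels shown separately;
- counts of events leading to dose reduction and to discontinuation;
- 0/N printed where no event occurred.

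Keep the listing. Label the table descriptive, and post hoc if it is added after database lock, with a note on the very low precision. If the table is not produced, state in the SAP why this commitment was dropped while the adverse event tables were kept.

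The cost is one table and a short attribution rule. The inputs are already collected: Protocol 5.5.5 requires the event and any dose change to be recorded, and SAP 6 lists dosing times and rates. The downside is one more table with wide uncertainty.
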